These results will help us:

- Establish feasibility of the hypothesis that VC will play a therapeutic role in treatment of PSC
- Gain insight into the effect of VC on profiles of the proinflammatory cytokines IL-17 and IFNy
- Pave the way for more comprehensive clinical studies

Study Design and Methodology

This pilot study will be a 6-month, 30-subject clinical trial to assess the effects of VC on a surrogate biochemical endpoint known to have relevant association with clinical outcomes in PSC. All endpoint tests chosen are rapid, inexpensive, and minimally invasive. Due to the low prevalence of PSC, the study will be a single-arm, open-label study. The study will be undertaken at two sites, Mayo Clinic, Rochester, Minnesota (20 subjects) and Mayo Clinic, Phoenix, Arizona (10 subjects), both of which are tertiary referral centers for PSC. Immunic AG, a biotechnology company based in Munich, Germany, will supply the study agent in sufficient quantities for the study (see Letter of Support from Immunic AG). We have confirmed through consultation with NIH personnel that this is permissible under this funding opportunity.

During the 6-month treatment period, subjects will receive 30 mg VC orally once daily, a dose determined to be both safe and therapeutically relevant based on previous clinical studies (see Table 1). This will be preceded by a lead-in dosing period where subjects will receive 15 mg VC once daily for 1 week. Lead-in dosing is used to minimize the risk of drug intolerance during the initial treatment period. While no clinically relevant adverse events have been noted at 30 mg once daily dosing, in rare instances potentially drug-related hematuria has been observed in the first few days of treatment at higher doses (≥ 70 mg/day). As a precaution, subjects will be monitored for two weeks after initial drug

exposure for elevated erythrocytes in the urine by a dipstick test. It is not anticipated that hematuria will be seen if it has not developed within the first two weeks of drug exposure.

The following endpoints will be assessed at various times during the study and compared with baseline:

- i. Primary endpoint:
 - a. Improvement of serum alkaline phosphatase (ALP) [baseline, 3 months, and 6 months]
- ii. Secondary endpoints:
 - a. Bilirubin, Total and Direct [baseline, 3 months and 6months]
 - b. AST and ALT (aspartate and alanine transaminases) [baseline, 3 months, and 6 months]

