 - c. Proinflammatory cytokine profile (IL-17 and IFN γ) [baseline, 4 weeks, and 6 months]

The most extensively studied surrogate endpoint in PSC is serum alkaline phosphatase (ALP). Our group at Mayo Clinic and others have reported an association between serum ALP and clinical outcomes in PSC. Specifically, normalization of serum ALP appears to be associated with long-term survival free of CCA, liver transplantation, liver-related death, and colorectal cancer and persistent ALP elevation has been associated with worse outcomes in PSC.⁵⁹⁻⁶¹ Therefore, we have chosen this simple, rapid, inexpensive, and minimally invasive test as our primary endpoint. AST, ALT, and bilirubin will be monitored to assess general liver health during the treatment. AST, ALT, or total bilirubin elevation can signal increased liver damage or liver cell necrosis, while elevated direct bilirubin may indicate bile duct obstruction. Further, it is hypothesized that treatment with VC will result in a reduction of IL-17 and IFN γ production. Levels of these cytokines will be measured at 4 weeks and at 6 months (end of study) and compared to baseline. The early 4-week time point will be used to determine whether early changes in these cytokines may predict improvements in ALP.

A 25% improvement in ALP with no more than a 33% worsening of AST after 6 months of treatment will be assessed as a positive outcome. While full normalization of ALP levels is unlikely over the short course of this pilot study, a 25% improvement would be deemed significant, indicating that VC has a positive effect on the progression of PSC. A less than 33% increase in AST levels concomitant with this ALP reduction would be acceptable, as it would be considered only a mild elevation. While a recent consensus statement from the International PSC Study Group indicates that transient elastography (TE), a new technique that allows non- invasive assessment of liver fibrosis, is one of the top three most promising surrogate endpoints for PSC (along with ALP and liver histology),⁶² it is unlikely that significant changes in TE would manifest in the 6-month course of this study. Thus, TE will not be included as an endpoint. Reduction of proinflammatory cytokines IL- 17 and IFN γ at the early 4-week time point concomitant with reduced ALP at the end of study would indicate a role for cytokine levels as an early predictor of improvements.

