Due to the relatively low prevalence, it is possible that 30 subjects meeting inclusion criteria cannot be recruited within the planned 6-month recruitment period or that they are not split roughly equally between the two sites. In that case, we will extend the recruitment period and if required, we will execute the study with as few as 20 subjects, regardless of the distribution between sites. After the study is complete, further research may reveal other potentially interesting biomarkers that should be examined and thus we have included storage of extra blood draws during the study. Given the pilot nature of this study, it is possible that benefits are seen even though results are not conclusive. Study data may be examined more carefully to determine if benefits occur in a distinct subpopulation of subjects (e.g. in PSC patients with UC versus those without).

Overall, considering the known safety data, the implemented risk minimization measures, the expected benefits in the target population, and the unmet medical need for treatment in PSC, the risk-benefit evaluation is considered favorable.

PROTECTION OF HUMAN SUBJECTS

This Human Subjects Research meets the definition of a clinical trial.

I. Risks to Human Subjects

a) Human Subjects Involvement, Characteristics, and Design: A total of 30 adults (age range 18-75 years) who meet the criteria for diagnosis of primary sclerosing cholangitis (PSC), as defined by the American Association for the Study of Liver Diseases (AASLD) published guidelines, will be enrolled into this study from two centers. PSC patients with and without inflammatory bowel disease (IBD) will be included. Other inclusion and exclusion criteria are detailed below:

Inclusion Criteria

- a. Male or female subject age 18-75 years
- b. Diagnosis of PSC consistent with the guidelines published by the AASLD. All subjects must have an elevated serum ALP of at least 1.5 times upper limit of normal (ULN) at baseline plus cholangiographic evidence of PSC (MRI, endoscopic retrograde cholangiography, or direct cholangiography).
- c. Indirect bilirubin <1.2 times the ULN
- d. An ultrasound (or equivalent imaging modality) that excludes biliary obstruction and malignancy within 6 months of study enrollment
- e. PSC with or without inflammatory bowel disease, such as ulcerative colitis or Crohn's disease
- f. Must agree to comply with the study protocol and provide informed consent

Exclusion Criteria

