A 25% improvement in ALP with no more than a 33% worsening of AST after 6 months of treatment will be assessed as a positive outcome. While full normalization of ALP levels is unlikely over the short course of this pilot study, a 25% improvement would be deemed significant, indicating that VC has a positive effect on the progression of PSC. A less than 33% increase in AST levels would be considered only a mild elevation and as such would be tolerable when accompanied by a concomitant reduction of ALP. While a recent consensus statement from the International PSC Study Group indicates that transient elastography (TE), a new technique that allows non-invasive assessment of liver fibrosis, is one of the top three most promising surrogate endpoints for PSC (along with ALP and liver histology), it is unlikely that significant changes in TE would manifest in the 6 month course of this study. Thus, TE will not be included as an endpoint.

Vidofludimus calcium will be supplied by Immunic AG, Munich, Germany throughout the full course of the clinical trial. It has been confirmed through consultation with NIDDK personnel that this is permissible under this funding opportunity and does not constitute undue involvement by a foreign component. As this is a single- arm pilot trial, no placebo will be used. All study medication will be manufactured, tested, and released according to current Good Manufacturing Practice guidelines and local requirements. The active ingredient is vidofludimus calcium. Inactive ingredients are microcrystalline cellulose EP, polyvidon K25, crospovidone EP type A, talc, and magnesium stearate. The tablet formulation consists of a specific polymorph of vidofludimus calcium. Tablets are white, uncoated, biconvex tablets with a diameter of 8 mm. The dosage strength will be 15 mg VC per tablet. Subjects will take one tablet once daily during lead-in dosing period and two tablets, once daily during the treatment period. A licensed pharmacist (designated by the co-investigator) at each research site's

pharmacy will be responsible for dispensing study medication. All study drugs will be labeled with "Caution: New Drug--Limited by Federal (or United States) law to investigational use" per 21 CFR 312.6.

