- Elevated total bilirubin $\geq 2 \times$ baseline that does not return to within 10% of baseline within two weeks
- Serious allergic reaction
- Pregnancy or breastfeeding

Non-adherence to the study protocol by a study subject may, at the discretion of the principal investigator, be grounds for termination.

Statistical Analysis Plan: The proportion of patients with normalization of serum ALP at 3 months and 6 months and their corresponding confidence intervals will be estimated using exact binomial method. The primary endpoint is ALP normalization (within the normal limits of the laboratory test) rate at 6 months. We will define success as a 95% CI that does not overlap 0 at 6 months. Further, we will further investigate if the absolute ALP decreases over time using mixed model with repeated measures to account for within patient correlation over time.

All the liver biochemistries and proinflammatory cytokine profile over time will be analyzed using mixed model with repeated measures to investigate how VC treatment plays a role over the 6 months duration. The liver biochemistries and proinflammatory cytokine will be dichotomized into abnormal and normal groups if possible and further the abnormal proportions at different time points will be estimated to see the trend over time.

The incidence, type and relatedness of serious adverse events and adverse events will be monitored and reported for all the subjects.

Adherence to Regulatory Standards: The investigators will ensure that this study is conducted in full conformity with Regulations for the Protection of Human Subjects of Research codified in 45 CFR Part 46, 21 CFR Part 50, 21 CFR part 56, and the ICH; Good Clinical Practice E6.

ClinicalTrials.gov Requirements: The principal investigator will ensure that this clinical trial is properly registered at www.clinicaltrials.gov, per the Public Law 110-85 (also known as the FDA Amendments Act (FDAAA) of 2007), no later than 21 days after the first subject is enrolled. The principal investigator will also ensure that the results (including adverse events) of this clinical trial are reported no later than 1 year after completion of the clinical trial.

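### The SAP's success rule is met by a single subject with normal ALP at month 6, so the chance of false success is neither controlled nor known

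*Combined protocol and SAP*

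**What the plan says.** In the Data and Safety Monitoring Plan, under Statistical Analysis Plan, the primary endpoint is the proportion of subjects whose ALP is within laboratory normal limits at 6 months. For the month-3 and month-6 proportions, "their corresponding confidence intervals will be estimated using exact binomial method". The decision rule follows: "We will define success as a 95% CI that does not overlap 0 at 6 months". A repeated-measures mixed model of absolute ALP is planned as further investigation, with no success rule attached.

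Other sections set the context:

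- Study Design and Methodology plans 30 subjects, and "the study will be a single-arm, open-label study".
- Risk Mitigation and Alternative Strategies adds that, if recruitment is slow, "we will execute the study with as few as 20 subjects".
- Inclusion Criteria: "All subjects must have an elevated serum ALP of at least 1.5 times upper limit of normal (ULN) at baseline".
- Study Design and Methodology, and again Risks to Human Subjects, describe the favourable result differently: "A 25% improvement in ALP with no more than a 33% worsening of AST after 6 months of treatment". Both sections also say that "full normalization of ALP levels is unlikely over the short course of this pilot study".
- The endpoint list in Study Design and Methodology gives the primary endpoint as improvement in ALP, and Aim 1 compares ALP levels at 3 and 6 months with baseline.

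The documents give no background or reference normalization rate, minimum count, type I error, power or sample-size justification.

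**The concern.** A confidence interval for a proportion cannot extend below zero. Asking that it exclude zero therefore tests only whether the true rate is exactly zero, and with an exact interval one event settles that. In a trial without a control arm, this benchmark does not separate a drug effect from normalization for any other reason.

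The documents themselves leave room for other reasons. The Significance section calls oral vancomycin a very promising PSC therapy, and Protections Against Risk allows it for *C. difficile* during the study. The same section allows relief of biliary obstruction. ALP may also vary on its own.

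The verdict on the primary endpoint could thus rest on one month-6 value in one subject. The section on the importance of the knowledge to be gained says the study should help decide whether larger trials are warranted, so a declared success has consequences.

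**Working it through.** The plan states no operating characteristic, so there is no figure to reproduce. The check rebuilds the rule from its own inputs.

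**Inputs.** Two-sided exact 95% interval, taken as Clopper-Pearson (Statistical Analysis Plan); n = 30 planned (Study Design and Methodology); n = 20 minimum (Risk Mitigation and Alternative Strategies); no subject normal at entry (Inclusion Criteria). The background rate p is not given and is assumed over a range.

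**Step 1: how many normalizers satisfy the rule.** With x = 0 the lower limit is 0 and the upper limit is 1 − 0.025^(1/n). With x = 1 the lower limit is 1 − 0.975^(1/n).

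| Normalizers | Exact 95% CI | Rule |
|---|---|---|
| 0/30 | 0 to 11.6% | not met |
| 1/30 | 0.08% to 17.2% | met |
| 0/20 | 0 to 16.8% | not met |
| 1/20 | 0.13% to 24.9% | met |

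Since 1 − 0.975^(1/n) is positive for every n, one normalizer is enough at any sample size. This depends on the method the SAP names. Wilson and Jeffreys intervals would also pass at 1; Agresti-Coull would need 2 and Wald 4.

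**Step 2: probability of success without a drug effect.** If each subject has probability p of a normal month-6 value regardless of the drug, then P(success) = 1 − (1 − p)^n. For example, p = 1% and n = 30 gives 1 − 0.99^30 = 26.0%.

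| Assumed p | n = 30 | n = 20 |
|---|---|---|
| 0.1% | 3.0% | 2.0% |
| 0.5% | 14.0% | 9.5% |
| 1% | 26.0% | 18.2% |
| 2% | 45.5% | 33.2% |
| 5% | 78.5% | 64.2% |

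**Step 3: background rate at which false success is 2.5%.** Solving 1 − (1 − p)^n = 0.025 gives p = 1 − 0.975^(1/n): 0.0844% (1 in 1,185) at n = 30 and 0.1265% (1 in 790) at n = 20.

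**Step 4: how far ALP must fall.** From the entry minimum of 1.5 × ULN to 1.0 × ULN is (1.5 − 1.0)/1.5 = 33.3%. This suggests a low background rate but does not supply one.

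**Step 5: what a non-zero reference rate p0 would require.** The table gives the smallest x whose exact lower limit exceeds p0, then the binomial upper tail P(X ≥ x) at p0 (type I error) and at the true rate (power). The p0 values are illustrations.

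| p0 | n | Needed (lower limit) | Type I error | Power at true rate |
|---|---|---|---|---|
| 1% | 30 | 3 (2.11%) | 0.3% | 59% at 10%; 96% at 20% |
| 1% | 20 | 2 (1.23%) | 1.7% | 61% at 10%; 93% at 20% |
| 5% | 30 | 5 (5.64%) | 1.6% | 18% at 10%; 48% at 15%; 74% at 20%; 97% at 30% |
| 5% | 20 | 4 (5.73%) | 1.6% | 13% at 10%; 35% at 15%; 59% at 20%; 89% at 30% |

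**The case against.** Under the rule's literal null, a true rate of exactly zero, false success cannot occur, so it could be said that the error is controlled. That is correct, but it restates the problem: zero is not a useful benchmark in a single-arm trial.

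No value of p in the table is supported by the documents. Entry at 1.5 × ULN or more, and the protocol's own remark that normalization is unlikely, point to the low end. This stands: the 79% figure is the top of an assumed range, not an estimate. Yet even 1% gives about one chance in four at n = 30.

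The study is a small exploratory pilot. No decision is tied mechanically to the success label, and the SAP already plans to report the proportion with its interval and to model absolute ALP. A reader shown 1/30 with its interval would see how little it supports. This lowers the stakes, but a formal success rule is still written down and would give an unsound verdict if followed.

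Finally, the 25% ALP criterion is partly a separate matter. The text does not say whether it applies to each patient or to the trial, so it need not be a rival success rule. That is fair, and the finding on the success rule holds without it. The relation between the two still has to be stated.

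**Conclusion.** The rule is wrong as written and must be fixed. At every sample size from 20 to 30, success means at least one normal month-6 ALP, and nothing else in the plan supplies a reference rate or minimum count. That part rests only on the exact binomial method named in the SAP.

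The size of the false-success risk cannot be fixed from the documents. Over assumed background rates of 0.1% to 5% it runs from 3% to 79% at n = 30 and from 2% to 64% at n = 20, treating subjects as independent with a common rate. The background rate may well be low, but the plan would have to show that it is below roughly 0.08% (n = 30) or 0.13% (n = 20) for the rule to hold false success to 2.5%.

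**What to change.** Choose one of two options before month-6 data are examined.

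**Option A.** Delete the success sentence and present the month-6 normalization rate with its exact 95% interval as an estimate. This is the sound default if no reference rate can be justified. It needs no extra patients, data or analysis; the cost is giving up a formal success claim.

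**Option B.** Define success as the lower limit of the exact 95% interval exceeding a pre-specified p0 above zero. Justify p0 from data outside these documents, and state type I error and power at n = 30 and n = 20. The cost is finding that source, a higher bar, and limited power for modest effects: with p0 = 5%, power at a true rate of 20% is 74% with 30 subjects and 59% with 20.

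Under either option, state how month-6 normalization relates to the criterion of 25% ALP improvement with at most 33% AST worsening, and say whether that criterion applies per patient or to the trial. Bring the primary endpoint in Study Design and Methodology, Aim 1 (stated in two places), and the matching text in Risks to Human Subjects into line, so that the trial has one primary criterion. This takes two or three sentences in the SAP and matching edits in those sections.
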